6.5.1 Objectives	13
6.5.2 Endpoints.....	14
6.5.3 Statistical Hypothesis, Model and Method of Analysis	14
6.6. Quality of Life	14

6.6.1 Objective.....	14
6.6.2 Endpoint	15
6.6.3 Statistical Hypothesis, Model and Method of Analysis	15
7. Sensitivity Analysis.....	15
8. Missing Data	15
9. References	15

1. Background and Study Design

The FILTER-SCAD trial is a randomized, controlled, multicentre, superiority trial with two parallel groups investigating the use of the acoustic measured risk score (CAD-score) for obstructive coronary artery disease (CAD) for ruling out CAD as compared to current standard diagnostic strategy in patients with symptoms suggestive of CAD.

Approximately 2000 patients with symptoms suggestive of CAD referred for outpatient assessment are expected to be enrolled at 5 study sites in Denmark and 1 in Sweden. The subjects will be randomized 1:1 to either 1) standard diagnostic strategy i.e. pre-test probability (PTP) stratification followed by non-invasive test (NIT), if indicated (control group), or (2) PTP plus CAD-score stratification followed by NIT, if indicated (intervention group). Randomization is stratified according to study site and PTP. Given the stratified design, all analyzes are carried out stratified by site and PTP.

2. Analysis Datasets

All patients from whom written informed consent are obtained will be included in the **full analysis set (FAS)**. Subjects will be analysed according to the allocated randomization group in accordance with the intention-to-treat principles.

The **per protocol set (PPS)** will include the subjects from the FAS who did *not* have one of the following major protocol violations:

- inclusion criteria not met
- exclusion criteria met
- no PTP calculation
- no CAD-score measurement (intervention group only).

Patients who did not receive the randomly allocated CAD-score measurement will be included and analysed in the control group (per protocol analysis).

The **screened analysis set (SAS)** will include all screened patients who receive a subject number.

3. Demographics and Baseline Characteristics

Continuous variables will be presented as mean and standard deviation for variables following a normal distribution or as median with interquartile range if showing a skewed distribution. Categorical variables will be presented as frequencies and percentages. Categorical data will be compared using Fisher's exact

test and continuous variables using T-test if normal distributed data or the Mann-Whitney U test. The analyses are performed on **FAS**, **PPS**, and **SAS**.

4. Primary Objective

The primary objective is to investigate if a combined PTP plus CAD-score guided rule-out strategy is superior in terms of reducing overall number of diagnostic procedures as compared to a standard PTP guided strategy when selecting patients with suspected stable CAD for NIT.

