4.2. Statistical Hypothesis, Model and Method of Analysis

Statistical Hypothesis

The statistical null hypothesis is that there is no difference between a PTP plus CAD-score guided rule-out strategy and a PTP guided strategy alone at one year in reducing diagnostic procedures (π) in patients with symptoms suggestive of stable CAD.

$$H_0: X/\pi_{PTP+CAD-score} = X/\pi_{PTP}$$

The alternate hypothesis is that a PTP plus CAD-score guided rule-out strategy is superior to a PTP guided strategy alone at one year in reducing diagnostic procedures (π) in patients with symptoms suggestive of stable CAD.

$$H_A: X/\pi_{PTP+CAD-score} \neq X/\pi_{PTP}$$

Statistical Model and Method of Analysis

The cumulative numbers of diagnostic test will be assessed using Poisson based test and visually by Nelson-Aalen nonparametric estimator.

Total numbers of patients undergoing diagnostic procedures will be presented as total numbers divided into categories of numbers of procedures: Categories: [0, 1, 2, 3+ diagnostic procedures].

The analyses are performed on **FAS** in accordance with the intention-to-treat principles.

A reduction of 15 % or more in the primary endpoint is regarded as clinically significant.

Sample size

A sample size of 521 provides 80 % power with an alpha significance level of 0.05 for testing superiority in terms of numbers of NIT between the control and intervention group.

The power calculation is based on the study design applicable when the study was initiated (Protocol version 3.0) which reflected the European guidelines from 2013 (Montalescot G *et al.* 2013). Protocol version 4.0 and 5.0 reflects the updated European guidelines from 2019 (Knuuti *et al.* 2019), however, the power calculation remains unchanged and a note provides an explanation for each section below.

The main analysis will be based on intention to treat. The study allows for some degree of cross-overs where patients ruled out instead are crossed-over to a NIT. The power calculation simulates a worst-case scenario where the two groups have the lowest expected difference in number of diagnostic procedures; 0% of patients with DF <15% crossed-over to NIT in the control group and 20% of patients with a CAD-score ruling out obstructive CAD in the intervention crossed-over to NIT.

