A reduction of 15% or more in the primary endpoint is regarded as clinically significant. Assuming an alpha significance level of 0.05, a statistical power of 80% and an expected number of NIT/ICA of 0.94 per patient in the standard care group, a sample size of 314 patients in each arm is needed to ascertain superiority of the intervention, in this case an absolute reduction in the primary endpoint of 0.17 NIT/ICA per patient, i.e. number of NIT/ICA.

The expected number of NIT/ICA of 0.94 in the control group and 0.77 in the intervention group is based on the following sequence of assumptions:

- No. of first NITs: n=760 in the control group (all patients with DF-score 15-85%) and n= 610 in the intervention group (all patients with a CAD-score not ruling out CAD + 20% of patients with a CAD-score ruling out CAD).
- No. of second NITs: 10% of first NIT; n=76 in the control group and n=61 in the intervention group.
- No. of ICAs: 10% of total population; n=100 in each group.

Note: the patient pathway is expected to change only slightly due to the updated ESC 2019 guidelines (Knuuti *et al.* 2019). Current data indicates that the number of patients in each arm will increase to 521 for the primary endpoint; which stays within the total number of 2000 patients as described below.

Given the abovementioned assumptions, the mean number of investigations (NITs and ICAs combined) per patient will be 0.94 in group 1 and 0.77 in group 2. A sample size of 314 patients in each arm will then provide 80% power for testing superiority in terms of number of diagnostic procedures for the group with CAD-score stratification compared to the group with DF-score only stratification, at an alpha significance level of 0.05.

The study allows for some degree of cross-overs where patients with PTP or CAD-score ruling out CAD instead are crossed-over to a NIT. The power calculation simulates a worst-case scenario where the two

groups (control and intervention group) have the lowest expected difference in number of diagnostic procedures; 0% of patients with low PTP ruling out CAD (Diamond-Forrester(DF) <15 %) crossed-over to NIT in the control and 20% of patients with a CAD-score ruling out CAD in the intervention group crossed-over to NIT.

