4.3. Subgroup Analysis

We will investigate the effect of a PTP plus CAD-score guided strategy versus a PTP guided strategy across the following pre-specified subgroups:

- PTP ($\leq 5\%$ vs. $>5-15\%$ vs. $>15\%$)
- PTP ($\leq 5\%$ vs. $>5\%$)
- PTP ($\leq 5\%$ vs. $>5-15\%$)
- Age (<65 y vs. ≥ 65 y).
- Sex (female vs. male).
- Hypertension (yes vs. no).
- Dyslipidaemia (yes vs. no).
- Diabetes mellitus (yes vs. no).
- Current/former smoker (yes vs. no).
- Family history of CAD (yes vs. no).
- Body mass index (<30 kg/m 2 vs. ≥ 30 kg/m 2).

Poisson-regression will be used in an interaction analysis. The interaction between the randomization variable and the subgroup variable will be investigated. The subgroup analysis will be made using both FAS and PPS.

5. Key Secondary Objective

The key secondary objective is to investigate if a combined PTP plus CAD-score guided rule-out strategy is non-inferior in terms of major adverse cardiac events (MACE) as compared to a standard PTP guided strategy when selecting patients with suspected stable CAD for NIT.

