5.2. Statistical Hypothesis, Model and Method of Analysis

Statistical Hypothesis

The statistical null hypothesis is a PTP plus CAD-score guided rule-out strategy is inferior in terms of safety outcomes MACE (π) in patients with symptoms suggestive of stable CAD at one year when using a pre-specified non-inferiority margin (δ) as compared to a standard PTP guided strategy.

$$H_0 = \pi_{PTP+CAD-score} - \pi_{PTP} \geq \delta$$

The alternate hypothesis is that a PTP plus CAD-score guided rule-out strategy is non-inferior to a standard PTP-guided strategy in terms of MACE in patients with symptoms suggestive of stable CAD at one year when using a pre-specified non-inferiority margin (δ).

$$H_A = \pi_{PTP+CAD-score} - \pi_{PTP} < \delta$$

Statistical Model and Method of Analysis

The absolute risk difference between treatment groups will be compared to a non-inferiority margin (δ) of 1.5% using a two-sided 95% confidence interval applying a continuity-corrected modification of the Wilson's score method. Based on previous studies (Therming *et al* 2018) the obstructive CAD prevalence is expected to be 6.5% and the event rate in each group is expected to be 1.3% at 1-year FU.

Moreover, data will be analyzed using stratified proportional hazard Cox regression and visually by Kaplan Meier curves.

Sample size

A sample size of 1914 provides 90% power with an alpha significance level of 0.05 for testing non-inferiority in terms of MACE between the control and intervention group.

This sample size calculation is based on the hypothesis of non-inferiority in terms of MACE in the group of patients with DF-score and CAD-score stratification prior to NIT compared with the group of patients with standard care strategy of DF-score stratification prior to NIT. It is assumed that in the control group, 50% of the patients with a DF-score <15% are ruled out of obstructive CAD without further testing, and 50% are referred for further testing. Based on previous studies (Therming *et al* 2018) the obstructive CAD prevalence is expected to be 6.5% and the event rate in each group is expected to be 1.3% at 1-year FU. The non-inferiority margin is set to 1.5%.

The assumed annual MACE event rates for different patient categories are:

- Clean arteries (CACS=0 and no stenosis): 0.4%

- Non-obstructive CAD: 1.2%
- Diagnosed CAD: 6.9%
- Unobserved CAD: 10.0%

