6.1.3 Statistical Hypothesis, Model and Method of Analysis

The statistical null hypothesis is that there is no difference between the two treatment arms with regards to symptoms. Within treatment group comparisons will be made with Wilcoxon signed rank test. Between treatment group comparisons will be made with Mann-Whitney U test.

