6.2. Investigations

6.2.1 objectives

- A. To investigate if the number of first NIT differ in the two treatment arms 1 year after randomization.
- B. To investigate if the number of downstream tests differ in the two treatment arms 1 year after randomization. Downstream tests defined as all NITs and ICA to detect CAD performed after a) PTP and first standard non-invasive testing and b) PTP, CAD-score and first non-invasive testing,

respectively, in the two groups. The term PTP refers to the DF-score for patients enrolled according to protocol version 3.0 and to the PTP in the ESC 2019 guidelines for patients enrolled according to protocol version 4.0 and 5.0, respectively.

- C. To investigate if the number of ICA differ in the two treatment arms 1 year after randomization.
- D. To investigate if the number of negative ICA differ in the two treatment arms 1 year after randomization. Classification of ICA results as positive, negative, or inconclusive will be done at each individual site according to local criteria/guidelines.
- E. To investigate if the number of repeat referrals differ in the two treatment arms 1 year after randomization.
- F. To investigate if the number of NIT performed after revascularization in the two treatment arms 1 year after randomization.

6.2.2 endpoints

- A. Difference between the two treatment groups in the number of first NIT, assessed at 1 year after randomization.
- B. Difference between the two treatment groups in the number of downstream tests, assessed at 1 year after randomization.
- C. Difference between the two treatment groups in the number of invasive coronary angiographies, assessed at 1 year after randomization.
- D. Difference between the two treatment groups in the number of negative invasive coronary angiographies, assessed at 1 year after randomization.
- E. Difference between the two treatment groups in the number of repeat referrals, assessed at 1 year after randomization.
- F. Difference between the two treatment groups in numbers of NIT performed after revascularization, assessed at 1 year after randomization.

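### Section 1 requires every analysis to be stratified by site and PTP, but the Fisher, Mann-Whitney and Wilson methods named later take no strata; and Fisher's test does not fit the count endpoints in 6.2

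*SAP*

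**What the plan says.** Section 1 sets a rule without exception, resting on randomisation by site and PTP: "Given the stratified design, all analyzes are carried out stratified by site and PTP".

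The method sections then read as follows.

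- 4.2, primary endpoint: "The cumulative numbers of diagnostic test will be assessed using Poisson based test". How strata enter, and which variance is used, is not stated. Section 4.3 adds: "Poisson-regression will be used in an interaction analysis".
- 5.2, MACE: non-inferiority is judged on a "two-sided 95% confidence interval applying a continuity-corrected modification of the" Wilson score method, with no strata mentioned. The supporting analysis does name them: "Moreover, data will be analyzed using stratified proportional hazard Cox regression".
- 6.3.3, time to rule-out and to diagnosis: Cox regression, again named as stratified.
- 6.1.3, chest pain: "Between treatment group comparisons will be made with Mann-Whitney U test". Sections 6.4.3 and 6.6.3 use the same test between arms.
- 6.2.3: Fisher's exact test for categorical data is the only method, although 6.2.2 defines endpoints A to F all as differences in numbers.
- 6.5.3: Mann-Whitney and Fisher's exact test.

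On the stratum itself, 6.2.1 says: "The term PTP refers to the DF-score for patients enrolled according to protocol version 3.0 and to the PTP in the ESC 2019 guidelines"; the latter applies under versions 4.0 and 5.0.

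**The concern.** Two things do not fit together.

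First, a programmer who runs Fisher, Mann-Whitney or the two-sample Wilson interval as named departs from Section 1. One who obeys Section 1 must replace each of them with a stratified counterpart that the SAP does not name. Because the word stratified is attached to Cox regression alone, the other sections look unstratified. The choice between the two would fall after data are available.

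Second, downstream tests (6.2 B), repeat referrals (E) and NITs after revascularisation (F) can each exceed one per patient. Fisher's test can be applied to them only after they are cut into categories, and 6.2.3 gives none; the 0, 1, 2, 3+ grouping in 4.2 is for presenting the primary endpoint. The test also yields no estimate of the difference in numbers that 6.2.2 sets as the endpoint.

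At stake are precision and a fixed analysis, not the false-positive rate.

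**Working it through.** **Inputs (SAP 4.2, 1000 patients per arm).** First NITs: "n=760 in the control group (all patients with DF-score 15-85"%), and 610 in the intervention group. Second NITs are 10% of first (76 and 61). ICAs are 100 per arm.

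**The plan's own figures.** (760+76+100)/1000 = 0.936, stated as 0.94. (610+61+100)/1000 = 0.771, stated as 0.77. Rate ratio 0.771/0.936 = 0.824.

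**Model-based Poisson.** SE of the log rate ratio = √(1/936 + 1/771) = 0.0486. Adding the PTP stratum leaves it at 0.049, so under this variance stratification gains nothing. Power at 1000 per arm: 0.165/√(1.707/1000) = 3.99, and Φ(3.99 − 1.96) = 97.9%.

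**Robust variance, no strata** (assumed: ICA independent of testing). Per-patient variance:
- control 0.76×1.3 − 0.836² + 0.1×0.9 = 0.379
- intervention 0.61×1.3 − 0.671² + 0.09 = 0.433

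The factor 1.3 is 0.9×1² + 0.1×2². SE = √(0.379/(1000×0.936²) + 0.433/(1000×0.771²)) = 0.0341. If ICAs occur only in tested patients, simulation gives 0.037.

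**Robust variance with the PTP stratum** (assumed split 760/240, nobody tested in the low stratum in either arm). Control: 0.76×(1.3 − 1.1² + 0.09) + 0.24×0.09 = 0.158. Intervention, with 610/760 = 0.803 tested: 0.76×(0.803×1.3 − (0.803×1.1)² + 0.09) + 0.24×0.09 = 0.291. SE = √(0.158/876 + 0.291/594) = 0.0259.

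**Other gradients.** These are simulated Poisson regressions with arm, then arm plus PTP. Each range covers the two ICA assumptions; all gradients are assumed.

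| Proportion with first NIT, high/low PTP | Robust SE narrowed by PTP |
|---|---|
| Control 100%/0%, intervention 80.3%/0% | 24-27% |
| Control 100%/0%, intervention 61%/61% | 6% |
| Control 100%/50%, intervention ×0.803 | 6-7% |
| Control 80%/50%, intervention ×0.803 | 2% |

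The first two rows give robust SEs of 0.034-0.037 without PTP and 0.026-0.035 with it. 95% intervals around 0.824, as 0.824×exp(±1.96×SE), are 0.75-0.91 model-based, 0.77-0.88 or 0.77-0.89 robust, and 0.78-0.87 to 0.77-0.88 robust with PTP.

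**First NIT as yes/no under the null.** The true size of a two-sided 5% Fisher test is about 4.3% with no PTP gradient, 3.5% at 80% v 50% tested, 2.5% at 90% v 50%, and 0.7% at 100% v 50% (20,000 simulated trials each; smaller repeat runs differ by up to about half a point). All lie below 5%.

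**Downstream tests (6.2 B)**, assuming every ICA follows a first NIT: 76+100 = 176 v 61+100 = 161 per 1000. The difference is 15, with half-width 1.96×√337 = 36, z = 15/√337 = 0.82 and power about 13%.

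**MACE.** At 13/1000 per arm the continuity-corrected interval is ±1.13 points. As an upper bound on any gain, suppose the strata separated patients perfectly into 6.5% with risk 10.0% and the rest with 0.4%. Then R² = 0.065×0.935×0.096²/(0.01024×0.98976) = 0.055, and 1.131×√(1 − 0.055) = 1.10 points.

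**6.4 B.** For an assumed 600/1000 v 550/1000, Mann-Whitney gives p = 0.0238 and chi-square p = 0.0237.

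**The case against.** The strongest reply is that Section 1 is a general rule that later sections need not repeat. For the primary endpoint this stands: a Poisson-based test can carry site and PTP, and 4.3 already uses Poisson regression. A reader might infer that the primary analysis contradicts Section 1; the text does not show that. What is open there is how the strata enter and which variance applies. The variance is a separate question, and most of the precision gain in the less extreme scenarios comes from it. The reply does not rescue Fisher, Mann-Whitney or the Wilson interval, because in their usual form they have no place for strata.

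It can also be said that PTP, though two scores by protocol version, is simply the score applied at enrolment, so that the analysis strata follow from the randomisation strata. That is a fair reading, and a few words would confirm it.

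On 6.2.3, the sentence speaks of categorical data and does not say that counts will be categorised. A reader might infer that the difference in numbers would never be reported. That does not follow: 6.2.2 defines the endpoints as such differences, and naming a test does not bar reporting them. The supported statement is that no fitting method is named. Fisher's test suits 6.2 A read as yes/no.

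Finally, Mann-Whitney for the proportion in 6.4 B might be called invalid. It is nearly a chi-square test on 0/1 data; it only lacks a risk difference. This mismatch is minor.

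**Conclusion.** The point holds in two parts. The rank, exact and Wilson methods do not follow the SAP's own rule on stratification, and 6.2.3 names no method that fits the count endpoints B, E and F.

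The consequence is loss of precision and an analysis left open. A reader might infer a raised false-positive rate; ignoring strata after stratified randomisation works the other way. On the primary planning figures, stratification as such narrows a robust standard error by about 2-7%. It reaches 24-27% only if no low-PTP patient is tested in either arm, whereas 5.2 assumes that half of the control patients with DF-score below 15% are referred on. Primary power is about 98% even with the model-based variance. For MACE the gain is negligible. For downstream tests, with about 13% power, what is missing is an estimate with its interval, not a likely significant result.

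These sizes rest on assumed PTP gradients, an assumed 760/240 split and assumed placement of ICAs. The textual conflict does not depend on them. The change should be made, but the trial's main conclusions do not hang on it.

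**What to change.** 1. Primary endpoint and the 6.2 count endpoints: Poisson regression with robust variance and terms for arm, site and PTP stratum as randomised. Report the rate ratio and the difference in mean number per patient, each with a 95% interval.
2. Binary endpoints (6.2 A as yes/no, 6.4 B, bleeding in 6.5 D): Cochran-Mantel-Haenszel test with a stratified risk difference.
3. Contrast and radiation dose, and the SAQ, HeartDiet and EQ-5D scores: van Elteren test between arms.
4. Amend the Section 1 sentence to exempt the MACE interval, the individual MACE components (6.5 A), device adverse events (6.5 E, intervention arm only by its endpoint definition) and the baseline comparisons in Section 3. There, events are too sparse or stratification is not needed. For MACE this changes wording only.
5. State a rule in advance for pooling sparse site-by-PTP cells, including for 6.2 F, which may have few events.

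The cost is SAP wording and modest programming on variables already used to randomise. The drawback is sparsity: 2000×1.3% = 26 expected MACE over 6 sites and an assumed 2-3 PTP strata (12-18 cells) is about 1.4-2.2 events per cell. That is why MACE is better exempted than stratified.

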6.6.3 Statistical Hypothesis, Model and Method of Analysis

The statistical null hypothesis is that there is no change in quality of life (QOL) from baseline to 3 months, and 1 year, respectively, after randomization (Quality of life will be assessed by the EuroQoL-5D).

Within and between treatment group comparisons will be made with Wilcoxon signed rank test and Mann-Whitney U test, respectively.

7. Sensitivity Analysis

A sensitivity analysis on all endpoints will be performed on patients enrolled according to protocol version 4.0 and 5.0 to investigate any potential differences in study results related to the change in study design due to the update of the European guidelines. The analyses will be performed using both PPS and SAS.

Heterogeneity in the treatment effect between sites and PTP groups will be investigated. An interaction analysis between the randomization variable and site will be made.

8. Missing Data

Data will be analysed for potential extreme outliers. If present, each outlier will be investigated.

However, outliers will be included in the analysis, except if a clinical cause can be excluded.

9. References

Task Force Members, Montalescot G, Sechtem U, Achenbach S, Andreotti F, Arden C, et al. 2013 ESC guidelines on the management of stable coronary artery disease: the Task Force on the management of stable coronary artery disease of the European Society of Cardiology. *Eur Heart J*. 2013 Oct;34(38):2949–3003

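### Section 2 excludes intervention patients without a CAD-score from the per-protocol set, then analyses the same patients as per-protocol controls

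*SAP*

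**What the plan says.** Section 2 of the SAP defines three analysis sets: the FAS, the PPS and the screened analysis set (SAS). For the FAS the rule is clear: "Subjects will be analysed according to the allocated randomization group in accordance with the intention-to-treat principles".

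The PPS consists of FAS subjects who did not "have one of the following major protocol violations". The last item on that list is "no CAD-score measurement (intervention group only"), so an intervention patient without a measurement is outside the PPS. The sentence directly after the list reads: "Patients who did not receive the randomly allocated CAD-score measurement will be included and analysed in the control group (per protocol analysis").

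The PPS is used in three places:

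- Section 3 runs the baseline comparisons on FAS, PPS and SAS.
- Section 4.3 states: "The subgroup analysis will be made using both FAS and PPS".
- Section 7 states: "A sensitivity analysis on all endpoints will be performed on patients enrolled according to protocol version 4.0 and 5.0", and on the sets to be used: "The analyses will be performed using both PPS and SAS".

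For the primary endpoint, section 4.2 specifies the FAS and says "The main analysis will be based on intention to treat". Section 5.2 names no analysis set for the MACE non-inferiority test.

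**The concern.** The list and the sentence after it deal with the same patients, under the same per-protocol label, and give opposite instructions. Two analysts working from section 2 could build different control arms and report different PPS results. With the choice left open, it could also be made after the results have been seen.

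The two rules are not equally sound. Reassignment mixes the randomised arms: the control arm would contain patients randomised to the intervention, selected because their measurement did not take place. Exclusion also selects after randomisation, and in one arm only, but it leaves the control arm as randomised.

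The stake is limited to supportive analyses. The most exposed is section 7, which covers all endpoints, MACE included, and is the SAP's check on whether the guideline change affected the results.

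**Working it through.** **The two rules side by side.** Take an intervention patient with no CAD-score and no other violation.

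| Rule in section 2 | In the PPS? | Analysed as |
|---|---|---|
| Violation list | No | Not analysed |
| Following sentence | Yes | Control |

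If the second rule prevails, the CAD-score item on the list excludes nobody and has no function. If the second rule was meant for a separate as-treated set, the SAP does not define one, and the sentence carries the per-protocol label.

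**Effect on arm sizes.** Take 1000 per arm (about 2000 patients, 1:1, section 1). At an assumed 5% without a score, exclusion gives 1000 controls against 950 intervention patients, and reassignment gives 1050 against 950. At 10% the figures are 1000 against 900, and 1100 against 900. The intervention arm is the same under both rules; only the control arm differs.

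**Inputs for the illustration**

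- Mean tests per patient, from the section 4.2 counts per 1000: control (760 + 76 + 100)/1000 = 0.936; intervention (610 + 61 + 100)/1000 = 0.771. These reproduce the SAP's 0.94 and 0.77. The randomised difference is 0.165. The counts rest on protocol 3.0 assumptions, so they only illustrate the section 7 population (protocol 4.0 and 5.0).
- MACE rate p = 1.3% in each arm and a margin of 1.5 percentage points (section 5.2).
- Assumed, because the SAP gives no value: share f of the intervention arm without a score, 5% or 10%; their mean number of tests m, 0.5 to 1.3; their MACE rate q, 0% to 4%.

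**Tests per patient, control minus intervention.** With equal arms the arm size cancels.

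- Reassigned: (0.936 + f·m)/(1 + f) − (0.771 − f·m)/(1 − f)
- Excluded: 0.936 − (0.771 − f·m)/(1 − f)
- Reassigned minus excluded: f·(m − 0.936)/(1 + f)

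For f = 0.05 and m = 0.5: reassigned is 0.961/1.05 − 0.746/0.95 = 0.915 − 0.785 = 0.130; excluded is 0.936 − 0.785 = 0.151.

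| f | m | Reassigned | Excluded | Reassigned minus excluded |
|---|---|---|---|---|
| 5% | 0.5 | 0.130 | 0.151 | −0.021 |
| 5% | 1.3 | 0.210 | 0.193 | +0.017 |
| 10% | 0.5 | 0.095 | 0.135 | −0.040 |
| 10% | 1.3 | 0.257 | 0.224 | +0.033 |

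Section 4.2 regards a reduction of 15% or more as clinically significant. In the first row the relative reduction is 0.151/0.936 = 16.1% under exclusion and 0.130/0.915 = 14.2% under reassignment. In that one scenario, the choice of rule alone decides on which side of the threshold the PPS estimate falls.

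**MACE risk difference, intervention minus control, at f = 5%**

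- Shift from the randomised difference if reassigned: 2f(p − q)/(1 − f²)
- Shift if excluded: f(p − q)/(1 − f)
- Reassigned minus excluded: f(p − q)/(1 + f)

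| q | Reassigned (points) | Excluded (points) | Reassigned minus excluded (points) |
|---|---|---|---|
| 0% | +0.130 | +0.068 | +0.062 |
| 1.3% | 0 | 0 | 0 |
| 4% | −0.271 | −0.142 | −0.129 |

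The direction depends on the unmeasured patients. If their risk is above average, both rules move the result towards non-inferiority, and reassignment moves it further.

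**The case against.** The best defence is that the later, more specific sentence qualifies the list. A patient who missed the measurement leaves the intervention arm and is analysed under the strategy actually received, which is pre-test probability without a CAD-score, the control strategy. On that reading this is loose drafting with an intent that can be guessed. The definition of the PPS does not support it, however: it admits only subjects without a listed violation, and the reading leaves the CAD-score item with no effect. Even if that was the intent, the result would be an as-treated comparison under a per-protocol label.

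Several narrower objections stand:

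- Only the control arm differs between the two rules.
- No confirmatory result is shown to depend on the choice. The primary test uses the FAS, the subgroup analyses are also run on the FAS, and section 5.2 ties the MACE test to no set.
- The decisive inputs are assumed. The cost of the ambiguity is reassigned minus excluded, which at 5% is at most about 13% of the planned difference in tests (0.021/0.165) and at most 0.13 points against the 1.5-point MACE margin. The larger MACE figure needs an event rate in the unmeasured patients about three times the planned 1.3%.
- Exclusion is itself a one-sided selection after randomisation, so keeping it does not make the PPS unbiased.
- Section 7 runs on PPS and SAS without the FAS, so it offers no FAS result in the same patients for the PPS to support.

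These points limit the consequence. They do not reconcile the two rules.

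**Conclusion.** The contradiction is real and can be seen from the text of section 2 alone. The reassignment sentence is also the wrong rule for a per-protocol set, because it moves patients between randomised arms on the basis of a post-randomisation event.

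The consequence is moderate. It reaches the PPS baseline tables, the PPS subgroup analyses and the section 7 sensitivity analysis, but not the primary analysis. Nothing is concluded about the section 5.2 MACE test. With 5% to 10% of the intervention arm lacking a score and 0.5 to 1.3 tests each, the choice of rule changes the difference in tests by between −0.040 and +0.033 per patient, against a planned 0.165. At 5% and an event rate of 0% to 4% in those patients, it changes the MACE risk difference by +0.06 to −0.13 points. These sizes are illustrations on stated assumptions; the contradiction does not depend on them. It should be fixed before the analysis.

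**What to change.** In section 2:

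- Delete the sentence that moves patients without a CAD-score to the control group, and keep the exclusion in the violation list.
- State that the PPS is analysed by randomised arm.
- State that this exclusion applies to one arm only and is a selection after randomisation, so PPS results are supportive to the FAS, where these patients remain in the intervention arm.

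If the reassigned comparison is wanted, define it as a separately named exploratory as-treated analysis, and say that it will not be used to support MACE non-inferiority. Adding the FAS to the sets named in section 7 would give the PPS results there an FAS counterpart in the same patients.

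The cost is one sentence deleted and two short statements added. The PPS loses the intervention patients without a CAD-score, whose number the SAP does not give. The sample size and the primary analysis do not change.
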